4.2.2 Exclusion Criteria

- 1. Current chronic use of NSAIDs, COX-2 inhibitors. We will allow prior use of those agents if patients stop them at least 2 weeks before accrual.
- 2. Is currently participating in a study of an investigational anti-cancer agent or receiving concurrent anti-cancer therapy for metastatic disease.

Protocol 2021-0077 Proprietary Information of MD Anderson PI: [name]

Co-PI: [name] Date: 11/22/2022

3. Has a diagnosis of immunodeficiency, or is receiving chronic systemic steroid therapy or any other form of immunosuppressive therapy.

- 4. Uncontrolled hypertension is defined as a systolic blood pressure > 150 mmHg or diastolic blood pressure > 90 mmHg, with or without antihypertensive medications.
- 5. Has a history of and/or active cardiac diseases.

History of cardiac diseases including:

- active myocardial infarction documented by elevated cardiac enzymes or persistent regional wall abnormalities on assessment of left ventricular function.
- history of documented chronic heart failure; and documented cardiomyopathy. Active cardiac diseases including:
- symptomatic angina pectoris within the past 180 days that required the initiation of or increase in anti-anginal medication or other intervention.
- ventricular arrhythmias except for benign premature ventricular contractions.
- supraventricular and nodal arrhythmias requiring a pacemaker or not controlled with medication.
- conduction abnormality requiring a pacemaker.
- valvular disease with documented compromise in cardiac function.
- symptomatic pericarditis.
- 6. Has preexisting neuropathy > Grade 2.
- 7. Patients with known hypersensitivity to halichondrin B and/or halichondrin B chemical derivative.
- 8. Has medical conditions requiring concomitant administration of strong CYP3A4 or P-glycoprotein inhibitors or inducers.
- 9. Potentially life-threatening second malignancy requiring systemic treatment within the last 3 years (i.e., patients with a history of prior malignancy are eligible if treatment was completed at least 3 years before entering the Treatment period and the patient has no evidence of disease) or which would impede evaluation of treatment response. Hormone ablation therapy is allowed within the last 3 years. Patients with history of prior early stage basal/squamous cell skin cancer or non-invasive or in situ cancers that have undergone definitive treatment at any time are eligible.
- 10. Known active central nervous system (CNS) metastases and/or carcinomatous meningitis. Subjects with previously treated brain metastases may participate if they are stable and have no evidence of new or enlarging brain metastases. They are not using steroids for at least 28 days before trial treatment.
- 11. Active infection requiring systemic therapy.
- 12. Known psychiatric or substance abuse disorders that would interfere with cooperation with the requirements of the trial.
- 13. Known active Hepatitis B or C.

Product: Grapiprant
Protocol 2021-0077 Proprietary Information of MD Anderson

PI: [name] Co-PI: [name] Date: 11/22/2022

4.3 Study Design

[figure not shown]
The design of this study is a single-arm, phase Ib/II study. The overview of the study is shown in **Figure 1**. A total of 25 patients will be enrolled in the study. Once the recommended phase II dose of grapiprant in combination with eribulin is determined, the remaining patients will be treated in the phase II portion, which adds 14 ± 2 days window period of grapiprant treatment alone before the main study to evaluate the effect of grapiprant treatment in the tumor microenvironment and urine prostaglandin E2 metabolite. We will perform a correlative study by collecting tumor and urine samples at pre-and post-window periods. We will ensure the safety of grapiprant and eribulin combination by phase Ib part and determine efficacy in the phase II part—the detail of the trial design described in the **statistical analysis plan (7.0)**.

The starting dose of grapiprant will be 300 mg BID daily orally. Eribulin will be intravenously administered on day 1 and day 8 of every cycle (starting at the FDA-approved dose of 1.4 mg/m²). We define one cycle as 21 days. We will continue the treatment until disease progression, discontinuation by severe toxicity, death, and patient withdrawal. If the patients cannot continue the eribulin because of its toxicity, they will stop eribulin but continue grapiprant as a single treatment until progression or discontinuation. If the patients cannot continue the grapiprant because of its toxicity, they will be off treatment. We will follow-up with the patients up to 5 years after off-treament (see section 4.9). The follow-up can be performed in the clinic in MD Anderson Cancer Center. If the patient is unwilling to come to the clinic, the follow-up would be done by phone.

We will perform imaging analysis by PET-computed tomography (CT) or CT/bone scan at baseline, after the 2 cycles of proposed treatment (does not includes window period), then at the end of every 3 cycles. The Quantitative Imaging Analyzing Core (QIAC) in MD Anderson Cancer Center will independently evaluate the treatment response based on the imaging results.

Protocol 2021-0077 PI: [name] **Proprietary Information of MD Anderson**

Co-PI: [name] Date: 11/22/2022

Product: Grapiprant

Protocol 2021-0077 Proprietary Information of MD Anderson

PI: [name] Co-PI: [name] Date: 11/22/2022

4.4 Treatment Plan

The dosing levels to be applied in this trial is outlined in **Table 1** below.

Table 1. Dosing level for grapiprant and eribulin in the phase Ib and II part

Phase Ib (dosing level)		Phase II (d	osing level)
Grapiprant	Eribulin	Grapiprant	Eribulin
(experimental)	(standard of care)	(experimental)	(standard of care)
300 mg BID, PO daily	1.4mg/m ² , iv, day 1	300 mg BID, PO daily	1.4mg/m ² , iv, day 1
(0)	and day 8 (0)	(to be determined by	and day 8 (0)
		phase Ib part)	
200 mg BID, po daily (-	1.1mg/m ² , iv, day 1	200 mg BID, po daily	1.1mg/m ² , iv, day 1
1)	and day 8 (-1)	(to be determined by	and day 8 (-1)
		phase Ib part)	
	0.7mg/m^2 , iv, day 1	100 mg BID, po daily*	0.7mg/m^2 , iv, day 1
	and day 8 (-2)		and day 8 (-2)

^{*}The dosing of 100 mg BID grapiprant will be used in phase II part only for the toxicity management.

4.4.1 Dose Selection

The RP2D of Grapiprant is suggested as 300 mg BID (twice a day) from the ongoing phase I clinical trial for colorectal cancer (CRC) and non-small cell lung cancer (NSCLC). Those trials observed acceptable tolerability when it was combined with an immune-checkpoint inhibitor. The most frequent adverse event was liver toxicity (elevated GGP and ALP). Also, a G2/3 hepatic event was observed for 18.5% at 300 mg BID in the CRC study and 14.3% in the NSCLC study (See the investigator brochure). Base on the result from phase I trials, we will start the grapiprant from 300 mg in phase Ib If we observe dose-limiting toxicity (DLT) with 300 mg BID, the dosing will go down to 200 mg BID and re-evaluate the safety (see the section of **statistical analysis plan [7.0]**). One cycle is defined as 21 days. Grapiprant will be administered orally every day of each cycle. A research medication diary will be used for source documentation. Patients will follow dosing instructions as below:

- Patients will take grapiprant daily as instructed dependent on their assigned dose. Patients are encouraged to take study drug with food or within 2 hours after eating as food is known to decrease common mild gastrointestinal adverse events in drugs of a similar class (COX-2 inhibitors). Patients are to maintain a normal diet.
- Patients should take grapiprant every 12 hours at approximately the same time each day and evening, and not to take more or less than the prescribed dose at any time.
- Patients should swallow the tablets whole and not chew, crush, or break them with about 8 oz water.
- The date, amount taken, and time of study drug administration will be recorded daily in a research medication diary.
- If vomiting occurs, the patient should not take a replacement dose but should attempt to take their next scheduled dose if they are able. Any dose variations due to vomiting should be recorded on the research medication diary.

Product: Grapiprant
Protocol 2021-0077 Proprietary Information of MD Anderson

PI: [name] Co-PI: [name] Date: 11/22/2022

• If the patient forgets to take a dose at the scheduled time, the patient can take the scheduled dose if less than 3 hours have passed from the regularly scheduled time. If more than 3 hours have passed after the scheduled time, then that missed dose should be omitted and the patient should continue treatment with the next scheduled dose. Any missed doses should be recorded in the research medication diary.

Eribulin 1.4 mg/m² will be administered on day 1 and day 8 of each cycle per institutional guidelines in the outpatient setting at MD Anderson or at the local clinic/hospital. The day 8 dose may be delayed for up to 1 week in patients with toxicities. Please refer to Table 3 for recommended eribulin dose modifications and criteria for treatment interruption and re-initiation with treatment-related adverse events. The toxicities requiring dose delays will be documented in the subject's chart.

4.4.2 Dose Modification

For patients who do not tolerate the protocol-specified dosing schedule, adjustments in grapiprant and eribulin doses are permitted to allow the patient to continue the study treatment. All dose modifications must be based on the worst preceding toxicity as graded by the NCI-CTCAE version 5.0. Those will also be counted as DLT when it meets DLT definition. The DLT will be defined as any of the following be "probable," "possible," and "definite events occurring in the first 21 days (cycle 1):

- Any Grade 3 hematologic toxicity with the following changes: grade 3 platelet count (< 50,000/mm³–25,000/mm³) with associated bleeding (without bleeding, grade 4 platelet count [< 25,000/mm³] will be defined as DLT); grade 3 absolute neutrophil count (<1,000–500/mm³) that persists for 7 or more days despite of the use of the grown factor support or that is associated with fevers (febrile neutropenia). (Otherwise, grade 4 absolute neutrophil count [< 500/mm³] will be defined as DLT.)
- Hepatocellular injury is indicated by 3-fold or greater elevations above the ULN of ALT or AST in addition to the elevation of serum total bilirubin > 2 x baseline. In such cases, no other reason can be found to explain the combination of increased transaminases and total bilirubin such as viral hepatitis, preexisting or acute liver disease, or another drug capable of causing the observed injury (Hy's Law). For patients with liver metastasis, 6-fold or greater elevations above the baseline of ALT or AST in addition to the elevation of serum total bilirubin > 4 x baseline.
- All other grade 3+ electrolyte abnormality associated with clinical symptoms, regardless of duration.
- Grade 3 nausea or vomiting that does not improve to Grade 1 within 72 hours of initiating supportive therapy.
- Any other non-hematologic grade ≥ 3 toxicity deemed to be related to the study drug that lasts 72 hours or more will be considered a DLT.
- A grade \geq 3 laboratory abnormality that is determined to be of no clinical significance by the investigators will not necessarily constitute a DLT.
- Any death not clearly due to the underlying disease or extraneous causes.

Dose modification at the time of toxicities will be conducted as follows:

Product: Grapiprant
Protocol 2021-0077 Proprietary Information of MD Anderson
[name]
Product: Grapiprant

PI: [name] Co-PI: [name] Date: 11/22/2022

Grapiprant

Safety management guidelines, including dose modification algorithms, are provided. Please note, in cases where the investigator is directed to permanently discontinue study treatment, these instructions are mandatory as described in this section. An overview of the available grapiprant dose modification guidelines is presented in **Table 1**. All AEs are to be graded according to NCI-CTCAE, version 5.0 (http://ctep.cancer.gov). All dose modifications and the reason(s) for the dose modification must be documented in the eCRF. The major classes of grapiprant toxicity described in **Table 2** include "Cardiac", "Blood pressure", and "Gastrointestinal", "Renal", and "Hepatic".

Investigators should refer to the grapiprant IB and Eribulin PI for additional information regarding the background of each drug and the management of other AEs or potential safety-related issues.

In case a dose reduction is necessary, the dose level or schedule of grapiprant may be changed as determined by the investigator and IKENA Oncology, consistent with the instructions for dose level and schedule (**Table 2**). If either study treatment is deemed intolerable and requires discontinuation despite optimal management, as described below, the participant must be discontinued from the study treatment, unless clinical benefit has been demonstrated. Any participant who requires a decrease in the grapiprant dose below 100 mg BID will discontinue grapiprant treatment and will come off study. Patients may continue to receive eribulin off study per standard of care if clinical benefit has been demonstrated per attending physicican discretion. Any participant that is required to discontinue eribulin for an AE may only continue on grapiprant if clinical benefit has been demonstrated and with agreement from the IKENA Oncology.

In the phase Ib part, we will set two dosing levels for grapiprant (300 mg and 200 mg). Grapiprant will start from 300mg BID daily and be initially tested in 3 patients. For the main study, we will set 2 dosing levels for grapiprant for dose reduction by the DLT in phase Ib part and 3 dosing levels for toxicity management in phase II part (**Table 1**). The major adverse events of grapiprant from previous clinical trials were not overlapped to those in eribulin; therefore, we will modify dosing based on the type of events. In the event of hepatic toxicity, we will modify the grapiprant first. The major reported adverse events for grapiprant from the phase I study include elevation of liver enzymes, colitis, myositis, and supraventricular tachycardia. The dosing modification for grapiprant will follow the instruction which is described later in this section. In case the patient had uncommon side effects, PI and clinical staff will discuss the event and determine which drug should be reduced dosing, the discussion of the event with the PI and the rationale (which drug to reduce) will be documented in the subject's chart. **Table 2** (grapiprant) and **Table 3** (eribulin) show the summary of dose modification and criteria for treatment interruption and re-initiation.

Table 2. Recommended grapiprant dose modifications and criteria for treatment interruption and re-initiation with treatment-related adverse events

DOSE MODIFICATIONS FOR GRAPIPRANT		
Toxicity (CTCAE 5.0 Grade)	Grapiprant Dose Modifications	
Non-Hematologic Adverse Events Not Otherwise Specified		
Grade 1	Administer symptomatic treatment as appropriate Continue study treatment at same dose	
	Follow-up:	

Product: Grapiprant
Protocol 2021-0077 Proprietary Information of MD Anderson
PI: [name]

Co-PI: [name] Date: 11/22/2022

	Symptoms resolve to baseline within 7 days:
	Provide close follow-up to evaluate for increased severity.
	Symptoms ongoing >7 days:
	Consider following algorithm for Grade 2 events.
Grade 2	Administer symptomatic treatment
	Investigate etiology
	Consider consulting subspecialist, biopsy, and/or diagnostic
	procedure
	Discuss with IKENA Oncology
	Follow-up:
	Symptoms ongoing >7 days or worsening
	• Consider interruption of study treatment
	• Resume study treatment at the same or lower dose if
	symptoms have improved to Grade 1
	* *
	• If potentially related to cumulative toxicity (past first cycle),
	consider changing administration of grapiprant to 2 weeks on/ 1 week off
	• If symptoms continue or worsen to Grade 3-4, follow
C 1. 2. 4	algorithm for Grade 3-4 events
Grade 3-4	Interrupt or discontinue study treatment
	Consult sub-specialist
	Discuss with IKENA Oncology
	Follow-up:
	Symptoms improve to Grade ≤ 1 :
	Restart study treatment at a lower dose of grapiprant
	• If potentially related to cumulative toxicity (past first cycle),
	consider changing administration of grapiprant to 2 weeks
	on/ 1 week-off
	Symptoms ongoing:
	• Discuss further management with consultant and IKENA
	Oncology
	Consider alternative therapy
CAPDIAC	
CARDIAC	
Arrhythmia (tachycardia: supravent	ricular tachycardia, atrial fibrillation)
	First Occurrence:
	Omit grapiprant
	Perform a repeat ECG within 1 hour of the first occurrence.
	Seek cardiologist input; address electrolytes, calcium, and
	magnesium abnormalities; concomitant medication must be
	reviewed.
	Second Occurrence:
	Permanently discontinue patient from grapiprant
Other Cardiac Events	
Grade 1 or 2	Continue study treatment at same dose
Orauc I Or Z	Commue study deathent at same dose

Product: Grapiprant
Protocol 2021-0077 Proprietary Information of MD Anderson
PI: [name]

Co-PI: [name] Date: 11/22/2022

Grade 3	Omit dose until resolved to ≤ Grade 1, then decrease 1 dose	
Grade 3	level	
Grade 4	Permanently discontinue patient from grapiprant	
BLOOD PRESSURE		
Hypertension * true uncontrolled hy warrant a dose reduction	pertension, not present at baseline, judged by the investigator to	
Grade 1: systolic BP (sBP) 120-139 mmHg or diastolic BP (dBP) 80-89 mmHg	Continue study treatment at same dose	
Grade 2: sBP 140-159 mmHg or dBP 90-99mmHg	Omit dose until resolved to ≤ Grade 1 Perform an ECG and seek cardiologist input per physician discretion; address electrolytes, calcium, and magnesium abnormalities; review concomitant medication. Once hypertension was resolved, the grapiprant may be restarted by decreasing 1 dose level. Continue measuring blood pressure daily at home.	
Grade 3: sBP ≥ 160mmHg or dBP ≥ 100 mmHg	Omit grapiprant Perform an ECG and seek cardiologist input per physician discretion; address electrolytes, calcium, and magnesium abnormalities; review concomitant medication. Permanently discontinue patient from grapiprant	
GASTROINTESTINAL		
Colitis		
Grade 1	Continue study treatment at same dose	
Grade 2	Omit dose until resolved to ≤ Grade 1, then restart at the same dose.	
Persistent > Grade 2 regardless of etiology	Permanently discontinue patient from grapiprant	
RENAL		
Serum creatinine		
< 2 x ULN	Continue study treatment at same dose	
2–3 x ULN	Omit dose until resolved to ≤ Grade 1, then resume	
HEPATIC		
Grade 1	Administer symptomatic treatment as appropriate Continue study treatment at same dose Follow-up:	
	Symptoms and laboratory abnormalities resolve to baseline within 7 days: Provide close follow-up to evaluate for increased severity Symptoms or laboratory abnormalities ongoing > 7 days: Consider following algorithm for Grade 2 events	

Co-PI: [name] Date: 11/22/2022

Product: Grapiprant

Grade 2	Administer symptomatic treatment Monitor liver chemistries (ALT, AST, bilirubin) weekly until they resolve, stabilize or return to within baseline Investigate etiology Consider consulting subspecialist, biopsy, and/or diagnostic procedure Discuss with IKENA Oncology Follow-up: Symptoms or laboratory abnormalities ongoing >7 days or worsening: Consider interruption of study treatment
	 If interrupted, when symptoms and laboratory abnormalities have improved to Grade 1, resume study treatment at a lower dose of grapiprant (≤200 mg Q12h following the first dose reduction, and ≤100 mg Q12h following the second dose reduction) With a second dose reduction, change administration of grapiprant to 2 weeks on/ 1 week off
	If symptoms continue or worsen to Grade 3-4, follow algorithm for Grade 3-4 events
Grade 3	Interrupt or discontinue study treatment Consult subspecialist Monitor liver chemistries (ALT, AST, bilirubin) at least twice weekly until they return to Grade 2, then follow Grade 2 guidelines Discuss with IKENA Oncology
	Follow-up: Symptoms and laboratory abnormalities improve to Grade ≤1: • Resume study treatment at a lower dose of grapiprant (≤200 mg Q12h following the first dose reduction, and ≤100 mg Q12h following the second dose reduction) • With a second dose reduction, change administration of grapiprant to 2 weeks on/ 1 week off
	 Symptoms or laboratory abnormalities ongoing >7 days after Interruption: Discuss further management with consultant and IKENA Oncology Permanently discontinue study treatment
Grade 4	Permanently discontinue study treatment Monitor liver chemistries (ALT, AST, bilirubin) at least twice weekly until they return to Grade 2, then follow Grade 2 guidelines Immediately inform IKENA Oncology and MD Anderson
	Follow-up:

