7.0 STATISTICAL ANALYSIS PLAN

The design of the present study is phase Ib/II. Previous phase I clinical trial conducted in colorectal cancer and non-small cell lung cancer has established P2RD as 300 mg BID when grapiprant was combined with an immune checkpoint inhibitor. DLT was not observed in the group with 300 mg BID, and the most frequent adverse event was the elevation of liver enzymes. We expect that even if grapiprant was combined with eribulin, the combination treatment will be safely administered; however, we will start the combination from the phase Ib part to ensure safety. The decision of deescalation is described in **Figure 2**. The maximum sample size of this study is **25 patients**.

In the phase Ib part, a safety lead-in to the phase II part, the three enrolled patients will initially start grapiprant with 300 mg BID every day and eribulin (1.4 mg/m², day 1 and day 8 of every cycle). We will monitor DLT during the 1st cycle of the treatment. If we observe < 2/3 DLT, we will enroll 3 more patients. If we observe 0 or 1/6 DLT, we will start phase II in that dose and roll over the patients to phase II. If we observe DLT \geq 2/3 or 2/6 patients, we will de-escalate the dosing to 200 mg BID. In de-escalation (200 mg cohort), if we observe < 2/3 DLT, enroll 3 more patients. If we observe 0 or 1/6 DLT, we will start phase II in that dose and roll over the patients to phase II. If we observe DLT \geq 2/3 or 2/6 patients, we will stop the safety trial.

For phase II, the same toxicities that are defined as DLT in phase Ib will be continuously monitored during the first cycle of treatment using the following safety rule: After the first 9 patients (including the first 6 patient rolled over from phase Ib part), if the grade 3/4 toxicity rate >30%, the investigators will inspect the totality of the safety data and potentially terminate the trial for safety.

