For each exploratory outcome measure (see 6.2, Biomarker Assessments), samples will be acquired pre- and post-treatment. Change associated with treatment will be assessed by t-test and regression models with relation to treatment time, with adjustment for relevant demographic and baseline covariates. A logistic regression model will be used to assess the association between objective response status and change in exploratory outcomes. A proportional hazard model will be used to assess the association between TTP, PFS, and OS with the change in urine prostaglandin E2 metabolite. Additional statistical methods may be used.

The Investigator is responsible for completing an efficacy/safety summary report and submitting it to the IND Office Medical Affairs and Safety Group, for review and approval.

Phase1b:

After the first 3 evaluable patients complete 1 cycle of study treatment, and every 3 patients thereafter. IND Office approval must be obtained, prior to expanding/changing dose levels.

Phase II:

Toxicity summary will be submitted after the first 9 evaluable patients (including the 6 patients treated at MTD), then every 6 evaluable patients complete 1 cycle of treatment.

Efficacy summary:

If the MTD is 300mg, summary will be submitted after 12 evaluable patients (including the 6 patients treated at MTD), complete 24 weeks of treatment and after the 25 evaluable patients complete 24 weeks cycles of treatment.

If the MTD is 200 mg, Summary will be submitted after 11 evaluable patients (including the 6 patients treated at MTD), complete 24 weeks of treatment, and after 25 evaluable patients complete 24 cycles of treatment.

A copy of the safety summary report should be placed in the Investigator's Regulatory Binder under "sponsor correspondence".

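### The phase II safety rule counts first-cycle events only, so toxicity in the 14-day grapiprant lead-in is recorded but does not enter the >30% trigger

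*Combined protocol and SAP*

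**What the plan says.** Section 4.3 states that phase II "adds 14 ± 2 days window period of grapiprant treatment alone before the main study". The phase II calendar (Section 4.13, Table 5b) puts this window in weeks 1–2 and cycle 1 in weeks 3–5. The phase Ib calendar has no such window.

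Section 4.4.2, like the synopsis, limits DLTs to "events occurring in the first 21 days (cycle 1"), with no separate definition for phase II. Section 7 carries this into phase II: "the same toxicities that are defined as DLT in phase Ib will be continuously monitored during the first cycle of treatment". The rule starts "After the first 9 patients (including the first 6 patient rolled over from phase Ib part") and asks for a review of all safety data, with possible termination, when the rate exceeds 30%.

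The reporting schedule at the end of Section 7 says "Toxicity summary will be submitted after the first 9 evaluable patients", then after every 6 evaluable patients who complete one cycle. Evaluable is defined for response (Section 4.9.2) but not for toxicity.

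Section 5.3.1 records adverse events from the first dose and evaluates for safety everyone who received any grapiprant. Section 4.8 allows termination at any time for unacceptable risk. Neither section brings lead-in events into the 30% count.

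**The concern.** The DLT wording fits phase Ib, where the first day of grapiprant is the first day of cycle 1. In phase II the two dates are about two weeks apart, and the counting period was not adapted. The gap covers the time when toxicity of grapiprant alone would first show. Phase Ib has not tested the lead-in sequence, because its six patients had none.

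Section 4.3 takes patients who cannot continue grapiprant for toxicity off treatment, so a patient who stops in the lead-in does not start cycle 1. If evaluable means having completed a cycle, that patient is missing from the numerator and the denominator. The data review that the rule calls for comes only after the threshold has been crossed, so it cannot make up for events that were never counted towards it.

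**Working it through.** **Which period is counted.** There are two readings of the DLT wording.
- *The 21 days are cycle 1.* This is what the parenthesis, the Section 7 rule and the calendar indicate. The 14 ± 2 lead-in days are then outside the count.
- *The 21 days run from the first grapiprant dose.* Then 21 − 14 = 7 days of the combination are covered (5 to 9 with the ± 2 days), and the rest of cycle 1 is outside.

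Either way, part of the 14 + 21 = 35 days from first dose to the end of cycle 1 is left out. The calculation uses the first reading.

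**Plan's own figures.** The documents give no operating characteristics for the safety rule, so there is none to reproduce. Table 7 concerns efficacy only; its rows reproduce and are not at issue here.

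**Inputs from the documents.**
- Threshold above 30%: at least 3 of 9 (2/9 = 22.2%, 3/9 = 33.3%), 5 of 15 (4/15 = 26.7%) or 7 of 21 (6/21 = 28.6%). The counts of 15 and 21 follow from the reporting schedule.
- Gate: "If we observe 0 or 1/6 DLT, we will start phase II in that dose and roll over the patients to phase II".
- New patients exposed to the lead-in: 3, 9 and 15 at the three counts.

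**Assumptions.** The documents give no lead-in rate for DLT-type events. I take a cycle-1 rate of 20% and a lead-in rate q of 2%, 5%, 10% or 15%, independent of cycle 1. The numerator is DLT-type events. When the lead-in is not counted, a patient lost there is replaced in the count by the next one who completes cycle 1.

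**Step 1, the gate.** P(0 of 6) = 0.8⁶ = 0.2621. P(1 of 6) = 6 × 0.2 × 0.8⁵ = 0.3932. The sum is 0.6554, so given that phase II opens the weights are 0.40 for no DLT and 0.60 for one.

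**Step 2, rate per new patient.** Not counted: 0.20. Counted: 1 − 0.80 × (1 − q), which is 0.216, 0.24, 0.28 and 0.32 for the four values of q.

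**Step 3, chance of crossing the threshold.** With k the threshold count and m the number of new patients, it is 0.40 × P(X ≥ k) + 0.60 × P(X ≥ k − 1), with X binomial in m.

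At 9 patients (m = 3, k = 3):
- Not counted: 0.40 × 0.008 + 0.60 × 0.104 = 0.0656.
- Counted, q = 15%: 0.40 × 0.0328 + 0.60 × 0.2417 = 0.1581.

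| Patients | Not counted | q = 2% | q = 5% | q = 10% | q = 15% |
|---|---|---|---|---|---|
| 9 | 6.6% | 7.6% | 9.3% | 12.4% | 15.8% |
| 15 | 5.9% | 7.6% | 10.5% | 16.6% | 24.0% |
| 21 | 4.4% | 6.1% | 9.5% | 17.2% | 27.2% |

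Each entry is the chance of being above the threshold at that count, not a cumulative chance.

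**Sensitivity at 9 patients, q = 10%.** With a cycle-1 rate of 10%, 1.2% against 4.2%; with 30%, 16.3% against 23.7%.

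**Structure of the first look.** With at most one event among the six roll-overs, reaching 3 of 9 takes events in at least 2 of the 3 new patients. Those three are exactly the patients whose lead-in events are outside the count.

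**The case against.** Lead-in toxicity does not go unseen. Adverse events are recorded from the first dose, and the calendar has adverse-event and laboratory checks at the start of the window and again at the start of cycle 1. The grapiprant dose-modification table is not restricted to cycle 1, and Section 4.8 permits termination at any time. Crossing 30% prompts a review, not an automatic stop. A reader might infer that the trial is blind to lead-in toxicity; the documents do not support that. What stands is narrower: these provisions are discretionary or descriptive, and none puts lead-in events into the one quantitative trigger.

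A reader might also infer that a patient who stops in the lead-in can never become evaluable for safety. That is not established. The rule itself speaks of the first 9 patients without an evaluability condition, and Section 5.3.1 evaluates all dosed patients. The exclusion is one reading of an undefined word in the reporting schedule.

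The assumed rates can be challenged too. Section 7 reports no DLT at 300 mg BID in the earlier studies. The 14.3% and 18.5% hepatic rates in Section 4.4.1 include grade 2, come from combination treatment and are not tied to a 14-day window. For that reason the range goes down to 2%, where the effect is small.

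A larger effect is tempting if the six roll-overs are treated as an unrestricted binomial sample: about 26% against 33–37% at 9 patients for lead-in rates of 10–15%. That includes outcomes with two or more DLTs in six, after which phase II would not open at that dose.

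Finally, counting the lead-in gives new patients about 35 days at risk against 21 for roll-overs, under an unchanged threshold. This stands as a cost of the change.

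**Conclusion.** The concern holds in this form: followed as written, the phase II rule omits DLT-type events from the lead-in, and the documents leave open whether patients who stop there are in the denominator. At an assumed 20% cycle-1 rate, counting the lead-in raises the chance of crossing the threshold at 9 patients from 6.6% to between 7.6% (lead-in rate 2%) and 15.8% (15%), and at 21 patients from 4.4% to between 6.1% and 27.2%. The omission rests on the text alone. Its size rests on the assumed rates, on independence of the two periods and on the 0-or-1-of-6 gate. The numbers are illustrations, not estimates for this drug. No figure stated in the plan is contradicted.

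**What to change.** Reconcile Sections 4.3, 4.4.2 and 7, including the reporting schedule:
- State that the phase II safety rule counts DLT-type events from the first grapiprant dose to the end of cycle 1.
- State that every patient who received any grapiprant is in the denominator, including those who stop in the lead-in, and define evaluable for the toxicity summary to match.
- Report lead-in and cycle-1 events separately as well, because the six roll-overs had no lead-in and the pooled rate mixes two exposure periods.

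The cost is a few sentences and no new data, since adverse events are already recorded from the first dose. The review trigger will fire more often at the unchanged 30% threshold, by the amounts tabulated above if the assumed rates apply. The counting period will be about 35 days for new patients against 21 days for roll-overs, which is why the separate display is needed.
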